9.3.3.1. ARANZ SilhouetteStarTM

The ARANZ measurement device is a portable device that easily allows capture of information about a patient's target wound. This information is analyzed, managed, and stored in a database on a secure device. Information captured includes photographic images, quantitative measures and other target wound assessment data input to the device by the clinician, all obtained with no contact with the patient's skin. ARANZ then builds that into an electronic record for printing and archiving. Information about the target wound's measurement history is available on this system so that the serial progression of the target wound status can also be calculated and presented.

The ARANZ measurement device has FDA 510(k) approval and is not being assessed for safety and efficacy in this study. The device is only being utilized to perform measurements.

Figure 9-3ARANZ SilhouetteStarTM

10. STUDY MEDICATION AND ADMINISTRATION

10.1. Study Medication and Administration

ZORBLISA will be supplied in 8-ounce tubes, to be reclosed after use and stored at room temperature.

ZORBLISA will be applied once a day to the entire body for a period of 1440 days (48 months).

The study cream will be returned at Visit 3, and all visits up to and including Visit 18 to evaluate compliance.

Additional information on the composition of the SD-101 dermal cream is contained in the SD-101 Investigator's Brochure.

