10.5. Treatment Accountability and Compliance Checks

The Sponsor or Designee will be responsible for performing drug accountability for the dermal cream. The medication provided for this study is for use only as directed in the protocol. It is the Investigator / Institution's responsibility to establish a system for handling study treatments, including investigational medicinal products, so as to ensure that:

- Deliveries of such products are correctly received by a responsible person
- Such deliveries are recorded
- Study treatments are handled and stored safely and properly as stated on the label
- Study treatments are only dispensed to study patients in accordance with the protocol
- Any unused products will be destroyed in accordance with CRO processes

At the end of the study, it must be possible to reconcile delivery records with records of usage and destroyed stock. Records of usage should include the identification of the person to whom the study treatment was dispensed, the quantity of the study cream and date of dispensing. This record is in addition to any drug accountability information recorded on the eCRF. Any discrepancies must be accounted for on the appropriate forms. Certificates of initial and any subsequent deliveries and destruction must be signed, preferably by the Investigator or a pharmacist, and copies retained in the Investigator Site File.

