11. STUDY SCHEDULE

Procedure Visit	1 Screening/Baseline	2 Month 1	3 Month 3	4 Month 6	5 Month 9	6 Month 12	7 to 17 Month 15 to 45 ^a (Every 3 months)	18 Month 48 Final Visit/ Early Termination
Study Day (± 7 Days for Visits 2 – 18)	0	30	90	180	270	360	450 to 1350	1440
Informed consent /assent signed	Х							
Inclusion/Exclusion assessment	Х							
Demographic, medical and medication history ^b	Х							
Physical examination ^c	Х							Х
Height, weight, and temperature ^c	Х							Х
Assess BSA of lesional skin ^d	Х	Х	Х	Х	Х	Х	Х	Х
Assess BSA of wound burden ^d	Х	Х	Х	Х	Х	Х	Х	Х
Assess target wound via ARANZ ^e	Х	Х	Х	Х	Х	Х	Х	Х
Bandage history	Х		Х	Х	Х	Х	Х	Х
Urine pregnancy test (females of child-bearing potential only) $^{\rm f}$	X		Х	Х	Х	Х	Х	Х
Dispense ZORBLISA ^g	Х		Х	Х	Х	Х	Х	
Collect ZORBLISA for the purpose of drug accountability			Х	Х	Х	Х	Х	Х
Collect all ZORBLISA								Х
Monitor adverse events ^h	Х	Х	Х	Х	Х	Х	Х	Х
Monitor use of concomitant medications	Х	Х	Х	Х	Х	Х	Х	Х

CONFIDENTIAL

- a. Patients will return once every 3 months for Visit 7 (Month 15; day 450), Visit 8 (Month 18; day 540), Visit 9 (Month 21; day 630), Visit 10 (Month 24; day 720), Visit 11 (Month 27; day 810), Visit 12 (Month 30; day 900), Visit 13 (Month 33; day 990), Visit 14 (Month 36; day 1080), Visit 15 (Month 39; day 1170), Visit 16 (Month 42; day 1260), and Visit 17 (Month 45; day 1350).
- b. Demographic, medical and medication history collected during SD-005 will be utilized as the baseline information for SD-006
- c. The physical examination, as well as, height, weight, and temperature performed at the final visit for SD-005 will be utilized as the baseline assessment for SD-006 unless Visit 1 is ≥ 14 days after the final SD-005 visit, in which case the assessment will be repeated. A complete physical examination, as well as, height, weight, and temperature will be performed at visit 18.
- d. The BSA assessments of lesional skin and wound burden performed at the final visit for SD-005 will be utilized as the baseline assessment for SD-006 unless Visit 1 is \geq 14 days after the final SD-005 visit in which case the assessment will be repeated. The BSA assessments of lesional skin and wound burden will be performed at visits 2 through 18.

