17.5. Data to be Considered as Source Data

The following are considered source data: Informed consents, laboratory reports, patient files, and IMP accountability list.

The following information must be entered in the patient's file:

- Patient's name, address and date of birth
- Patient's weight, height, and temperature
- Medical history
- Bandage history including (type of bandage used and frequency of usage)
- Concomitant medication
- Unambiguous reference to the clinical study (clinical study number, screening number and patient number)
- Information on main selection criteria (diagnosis)
- Dates of study drug administration and amount of drug used/returned by the patient
- Date of informed consent / assent
- Physical examinations and results done at the appropriate visits
- Dates and time of urine pregnancy test
- Anatomical location of the target wound and corresponding ARANZ report with photograph
- Did AE(s) occur, improve or worsen?
- Date of discontinuation / completion of the clinical study.
- For patients that are lost to follow-up, the site is to document attempts made to contact the subject *i.e., telephone, email, certified letter*

All other data recorded directly in the eCRF [*i.e.*, no prior written or electronic record of data] will be considered as source data.

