6.5. Safety Assessments

6.5.1. Extent of Exposure and Compliance to Study Treatment

SD-101-6.0 will be applied once a day to the entire body for a period of 1440 days. No daily use data are collected in this study.

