8.7. Analysis of Safety

8.7.1. Extent of Exposure

No diary data were collected on whether a patient used or did not use SD-101-6.0 on a given day. Therefore the number of days on the study will be considered number of days of exposure. It will be summarized using descriptive statistics by overall. Descriptive statistics will also be provided for duration of exposure into categorical summary of <30, >=30 to <90, >=90 to <180, >=180 to <1 year, >=1 year to <2 years, >=2 years.

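### The SAP counts every day on study as a day of exposure, which is only an upper limit on days of application, and it leaves the returned-cream data unused

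*Protocol*

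**What the plan says.** The protocol provides for information on use of the cream in four places.

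- Section 10.1: "The study cream will be returned at Visit 3, and all visits up to and including Visit 18 to evaluate compliance".
- Section 11, the schedule, has a row for the same visits: "Collect ZORBLISA for the purpose of drug accountability".
- Section 10.5 requires usage records that can be reconciled with deliveries, and adds: "This record is in addition to any drug accountability information recorded on the eCRF".
- Section 17.5 lists among the items that must be in the patient's file: "Dates of study drug administration and amount of drug used/returned by the patient".

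The SAP has a section, 6.5.1, whose title covers both exposure and compliance. It defines no compliance measure and says only: "No daily use data are collected in this study". Section 8.7.1 gives the reason for its rule, "No diary data were collected on whether a patient used or did not use SD-101-6.0 on a given day", and then the rule: "Therefore the number of days on the study will be considered number of days of exposure". Duration is then grouped into categories, of which the last two are ">=1 year to <2 years, >=2 years".

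No SAP section summarises or lists returned cream, amount used or compliance. SAP 5.2, which records changes from the protocol's planned analyses, does not mention that the compliance evaluation was left out.

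**The concern.** The lack of a diary means that daily use is not known. It does not remove the other sources on use that the protocol requires: application dates and amounts returned. The SAP goes from having no diary to treating every day as treated, and passes over what lies between.

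Long-term safety is the primary objective, and the exposure table tells a reader how long patients were actually treated. If it counts untreated days, some patients will appear in a longer category than their treatment supports. Without any measure of use over time, a reader also cannot tell good tolerability from declining use.

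**Working it through.** **Planned duration.** 48 months x 30 days = 1440 days, as stated in Protocol 10.1. Cream is dispensed at Visit 1 but not at Visit 2, and is returned at Visits 3 to 18. That gives 18 - 3 + 1 = 16 dispensing intervals of 90 days, and 16 x 90 = 1440. The planned returns therefore cover the whole treatment period.

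**What the day count includes.** SAP 8.7.1 does not define the first and last day on study. I take the first from SAP 6.2.1, where study day 0 is the consent date, and the last as the final visit. Apart from a one-day counting convention, this count can exceed application days in SD-006 but cannot fall short of them. There are three sources of excess:

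1. Days from consent to first application. SAP 8.7.2 allows for such a gap, since it classes adverse events that start within it as not treatment-emergent. It may be short or zero.
2. Days from last application to last visit. SAP 5.1 reports that sites were told on June 4, 2018 to stop application immediately and bring patients back for an end-of-study visit. For patients then on treatment who came back later, these days are untreated but counted.
3. Missed days during treatment. Their number is unknown.

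**Size of source 2.** With T days on study and an untreated gap of L days at the end, the over-count is L/(T - L). The documents do not give L, so the values below are assumptions.

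| Assumed gap L | T = 360 days | T = 720 days |
|---|---|---|
| 7 days | 7/353 = 2.0% | 7/713 = 1.0% |
| 30 days | 30/330 = 9.1% | 30/690 = 4.3% |
| 90 days | 90/270 = 33.3% | 90/630 = 14.3% |

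Taking two years as 730 days, a patient with a 30-day gap and 730 to 759 days on study is placed in the top category with only 700 to 729 days from consent to last application.

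**Size of source 3, for illustration only.** If a fraction a of days is treated, the over-count is 1/a - 1. For assumed values of 95%, 90%, 80% and 50%, this gives 5%, 11%, 25% and 100%. At 80%, 730 days on study correspond to 0.80 x 730 = 584 application days. Reaching 730 application days would take 730/0.80 = 912.5, so 913 days on study. Nothing in the documents says which value of a applies.

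**Where the error goes.** SAP 8.7.3 and 8.7.5 report adverse events as numbers and percentages of patients and as numbers of events. None of these is divided by exposure time. The error therefore reaches the duration summary and its categories, and no adverse event figure.

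**Dates available.** SAP 6.2.1 and the date-imputation rules in 6.5.2 already use the date of first study drug administration. The concomitant-medication rule in SAP 8.5 already refers to the last dose.

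**The case against.** The strongest case on the other side is that the SAP states its rule and the reason for it openly, so no reader is misled. Returned cream also has an operational use: both schedules give its purpose as accountability, and Protocol 15 allows withdrawal for significant noncompliance. Such withdrawals would appear in the disposition summaries. The one statement on adherence in the documents, in Protocol 5.2 for an earlier open-label study of eight patients treated for up to three months at 3%, reports good compliance. And returned cream gives an amount. With no expected daily amount stated, and patients of all ages, it cannot be turned into days, nor can it separate skipped days from thinner or partial application.

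Much of this stands, and it limits the point. A reader might infer that exposure is overstated by 25% to 100%, and that adverse event rates per day of use are understated by 20% to 50%. The documents support neither. The first needs an adherence of 50% to 80% that is pure assumption, and the second concerns a statistic that the SAP does not plan. Nor is cumulative exposure necessarily overstated for every patient: those who received SD-101-6.0 in SD-005 have earlier exposure that the SD-006 count leaves out.

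Two things remain. Stating the rule openly does not make days on study equal to days of treatment, and SAP 5.1 itself describes a stop in application that precedes the last visit. In addition, the protocol promised a compliance evaluation, and the SAP neither performs it nor records that it was dropped.

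**Conclusion.** The point holds in a limited form and is minor. Days on study is an upper limit on application days in SD-006, and the SAP presents it as exposure. The excess from consent and from the 2018 stop follows from the documents' own rules, although its size depends on gaps that they do not give: 1.0% to 14.3% at 720 days on study, and 2.0% to 33.3% at 360, for assumed gaps of 7 to 90 days. Any excess from missed days is possible but unknown. What is affected is the exposure-duration table, its categories and the reading of the long-term safety conclusion. The planned adverse event percentages and counts are not affected. This rests on reading days on study as running from consent to the last visit.

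**What to change.** In SAP 8.7.1:

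- Compute duration of exposure as last application date minus first application date plus 1. Use the last visit only where the last application date is unknown, and flag those patients.
- Keep days on study as a second line, labelled as time on study (maximum exposure), with a footnote that exposure in SD-005 is not included.
- From the accountability data, summarise amount dispensed minus amount returned per dispensing interval, divided by the days in the interval. Show it by prior treatment group and by the age groups of SAP 7.6, with unreturned tubes counted as missing.

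If the amounts did not reach the database, which the documents leave open, record in SAP 5.2 that the compliance evaluation of Protocol 10.1 was dropped and why.

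I would not scale the amount to body surface by interval, because height and weight are scheduled only at Visit 1 and at Visit 18 or early termination, and many patients may be growing children.

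The first two changes use dates that the SAP already relies on and cost little. The third is one further table if the amounts are in the database. Its weakness is that returned amount is a rough measure of use and cannot be converted into application days.

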10.2. Selection of doses in the study

All patients will receive ZORBLISA (containing 6% allantoin) daily.

10.3. Allocation to Treatment

All patients will receive open-label ZORBLISA.

10.4. Duration of Patient Participation

It is anticipated that each eligible subject will participate in the trial for approximately 1440 days. This study may be further extended by amendment until either SD-101 becomes commercially available or the clinical development of SD-101 in EB is discontinued.

10.5. Treatment Accountability and Compliance Checks

The Sponsor or Designee will be responsible for performing drug accountability for the dermal cream. The medication provided for this study is for use only as directed in the protocol. It is the Investigator / Institution's responsibility to establish a system for handling study treatments, including investigational medicinal products, so as to ensure that:

- Deliveries of such products are correctly received by a responsible person
- Such deliveries are recorded
- Study treatments are handled and stored safely and properly as stated on the label
- Study treatments are only dispensed to study patients in accordance with the protocol
- Any unused products will be destroyed in accordance with CRO processes

At the end of the study, it must be possible to reconcile delivery records with records of usage and destroyed stock. Records of usage should include the identification of the person to whom the study treatment was dispensed, the quantity of the study cream and date of dispensing. This record is in addition to any drug accountability information recorded on the eCRF. Any discrepancies must be accounted for on the appropriate forms. Certificates of initial and any subsequent deliveries and destruction must be signed, preferably by the Investigator or a pharmacist, and copies retained in the Investigator Site File.

10.6. Concurrent Therapy

Medications considered necessary for the subject's welfare may be given at the discretion of the investigator. The administration of all such medication / therapy must be recorded in the appropriate section of the eCRF.

11. STUDY SCHEDULE

Procedure Visit	1 Screening/Baseline	2 Month 1	3 Month 3	4 Month 6	5 Month 9	6 Month 12	7 to 17 Month 15 to 45 ^a (Every 3 months)	18 Month 48 Final Visit/ Early Termination
Study Day (± 7 Days for Visits 2 – 18)	0	30	90	180	270	360	450 to 1350	1440
Informed consent /assent signed	Х							
Inclusion/Exclusion assessment	Х							
Demographic, medical and medication history ^b	Х							
Physical examination ^c	Х							Х
Height, weight, and temperature ^c	Х							Х
Assess BSA of lesional skin ^d	Х	Х	Х	Х	Х	Х	Х	Х
Assess BSA of wound burden ^d	Х	Х	Х	Х	Х	Х	Х	Х
Assess target wound via ARANZ ^e	Х	Х	Х	Х	Х	Х	Х	Х
Bandage history	Х		Х	Х	Х	Х	Х	Х
Urine pregnancy test (females of child-bearing potential only) $^{\rm f}$	X		Х	Х	Х	Х	Х	Х
Dispense ZORBLISA ^g	Х		Х	Х	Х	Х	Х	
Collect ZORBLISA for the purpose of drug accountability			Х	Х	Х	Х	Х	Х
Collect all ZORBLISA								Х
Monitor adverse events ^h	Х	Х	Х	Х	Х	Х	Х	Х
Monitor use of concomitant medications	Х	Х	Х	Х	Х	Х	Х	Х

CONFIDENTIAL

- a. Patients will return once every 3 months for Visit 7 (Month 15; day 450), Visit 8 (Month 18; day 540), Visit 9 (Month 21; day 630), Visit 10 (Month 24; day 720), Visit 11 (Month 27; day 810), Visit 12 (Month 30; day 900), Visit 13 (Month 33; day 990), Visit 14 (Month 36; day 1080), Visit 15 (Month 39; day 1170), Visit 16 (Month 42; day 1260), and Visit 17 (Month 45; day 1350).
- b. Demographic, medical and medication history collected during SD-005 will be utilized as the baseline information for SD-006
- c. The physical examination, as well as, height, weight, and temperature performed at the final visit for SD-005 will be utilized as the baseline assessment for SD-006 unless Visit 1 is ≥ 14 days after the final SD-005 visit, in which case the assessment will be repeated. A complete physical examination, as well as, height, weight, and temperature will be performed at visit 18.
- d. The BSA assessments of lesional skin and wound burden performed at the final visit for SD-005 will be utilized as the baseline assessment for SD-006 unless Visit 1 is \geq 14 days after the final SD-005 visit in which case the assessment will be repeated. The BSA assessments of lesional skin and wound burden will be performed at visits 2 through 18.
- e. If the target wound has not healed by the final visit of the SD-005 study, the target wound will be assessed in SD-006 using ARANZ until the wound has healed. The ARANZ picture and target wound area value determined at the final visit for SD-005 will be utilized as the baseline target wound area and picture for SD-006 unless Visit 1 is ≥ 14 days after the final SD-005 visit, in which case the assessment will be repeated. If target wound has healed, assess for scarring.
- f. The urine pregnancy test performed at the final visit for SD-005 will be utilized for entry into SD-006 if the visits occur on the same day. Otherwise, the urine pregnancy test will be performed at Visit 1 and at Visits 3 through 18.
- g. Ensure the patient is dispensed sufficient ZORBLISA until the next study visit.
- h. All AEs experienced in SD-005 should be noted in medical history for SD-006 at Visit 1 only.

12. EFFICACY ASSESSMENTS

The body surface coverage (BSA) of lesional skin and wound burden will be measured at each visit via the BSAI as described in Sections 9.3.1 and 9.3.2 to monitor the extent of coverage with extended use of ZORBLISA.

Any target wound not completely healed during the SD-005 study will continue to be monitored for closure at each study visit, as described in Section 9.3.3.

13. SAFETY ASSESSMENTS

The safety of ZORBLISA applied to the skin will be assessed by monitoring tolerability at the application sites, adverse events, and physical examinations.

For timing of individual measurements, refer to Section 11 - Study Schedule.

13.1. Physical Examination including Height, Weight, and Temperature

The physical examination performed at the final visit for SD-005 will be utilized as the baseline assessment for SD-006 unless Visit 1 is \geq 14 days after the final SD-005 visit, in which case a physical examination will be repeated An additional physical examination will be done by a physician at Visit 18. The following sites will be examined: head, eyes, ears, nose, throat, neck, chest, lungs, heart, abdomen, skin, and lymph nodes; and the following systems will be assessed: musculoskeletal and neurological. Weight, height, and temperature will be recorded.

13.2. Urinalysis

The urine pregnancy test performed at the final visit for SD-005 will be utilized for entry (Visit 1) into SD-006 only if the visits occur on the same day, otherwise, urine pregnancy test will be performed at Visit 1. Urine pregnancy tests for female patients of child bearing potential (sensitivity at least 25 mIU/ml) will also be performed at Visit 3 through 18.

13.3. Adverse Events

Adverse events may be volunteered spontaneously by the patient or discovered as a result of general, non-leading questioning. All adverse events should be recorded in the Case Report Form. Adverse events will be collected after signing the informed consent/assent through Visit 18. Information on AEs will be followed to 30 days after the last dose of study drug has been administered.

In the case of withdrawal due to an AE/SAE, the patient will be followed until resolution of the AE, or until in the opinion of the Investigator the event has stabilized, or the investigator does not expect any further improvement or worsening of the subject's condition, and the patient is referred to their primary physician for appropriate management of the ongoing event. Reasonable efforts will be made to contact a patient who fails to attend any follow-up appointments, in order to ensure that he/she is in satisfactory health.

Note: All AEs experienced in SD-005 and medical events occurring between the end of SD-005 and the enrollment into SD-006 after completion of SD-005 should be noted in the medical history for SD-006 at Visit 1 only.

13.3.1 Definitions

Adverse Event (AE)

Any untoward medical occurrence in a patient, administered a medicinal product and which does not necessarily have to have a causal relationship with this treatment. An adverse event (AE) can therefore be any unfavorable and unintended sign (including an abnormal laboratory finding, for example), symptom, or disease temporally associated with the use of a medicinal product, whether or not considered related to the medicinal product. AEs may include the onset of new illness and the exacerbation of pre-existing conditions.

The routine evolution of the disease condition under treatment according to the protocol will be evaluated as part of the disease symptoms assessments. Changes in the disease condition may not qualify as AEs. However, if there is a clinically relevant worsening of a sign or symptom of the condition under treatment and the outcome fulfills the definition of an AE, it must be reported as directed in the protocol.

Adverse Drug Reaction (ADR)

All events considered to be noxious and unintended responses to a medicinal product related to any dose should be considered adverse drug reactions, with the exception of skin site changes captured during the skin site evaluations (refer to Section 9.3). A lack of efficacy (i.e. worsening EB) should not be considered an ADR. Changes outside of the intended effect (e.g. rash) should be considered ADRs. The phrase "responses to a medicinal product" means that a causal relationship between a medicinal product and an adverse event is at least a reasonable possibility, i.e., the relationship cannot be ruled out.

Serious Adverse Event (SAE)

An adverse event that:

- Results in death
- Is life-threatening (i.e. the patient was at risk of death at the time of the event; it does not refer to an event which hypothetically might have caused death if it was more severe)
- Results in hospitalization or prolongation of existing hospitalization
- Results in persistent or significant disability/incapacity
- Is a congenital anomaly / birth defect
- Is considered to be an important medical event

Based upon medical and scientific judgment, important medical events that may not be immediately life-threatening, or result in death or hospitalization, but may jeopardize the patient or may require intervention to prevent one of the other outcomes listed in the definition above may be considered a serious adverse event.

Hospitalizations are defined as initial or prolonged admissions that include an overnight stay. Hospitalization or prolonged hospitalization for technical, practical or social reasons, in the absence of an adverse event is not an SAE.

Pregnancy

Pregnancy itself is not considered an AE. Pregnancies will be reported and documented on a separate pregnancy report form provided to the sites. However, any pregnancy complication, spontaneous or elective abortion, still birth, neonatal death, or congenital anomaly will be recorded as an AE or SAE.

Unexpected Adverse Drug Reaction

An adverse reaction, the nature or severity of which is not consistent with applicable product information (*e.g.*, Investigators Brochure).

Suspected Unexpected Serious Adverse Reaction (SUSAR)

A SUSAR is a serious adverse event that is suspected to be related to the administered medicinal product and the nature or severity of which is not consistent with applicable product information.

